7.3 RECORDS RETENTION17

8 STUDY FINANCES 18

8.1 FUNDING SOURCE 18
8.2 CONFLICT OF INTEREST 18
8.3 SUBJECT STIPENDS OR PAYMENTS 18
8.4 REGULATORY INFORMATION 18
9 REFERENCES 19

LIST OF ABBREVIATIONS

AE	Adverse Event/Adverse Experience
HIPAA	Health Insurance Portability and Accountability Act
PTT	Penile traction therapy
PD	Peyronie's Disease
RCT	Randomized controlled trial

Study Summary

Title	Penile Lengthening Maintenance Post-prostatectomy
IRB Protocol Number	18-001013
Methodology	Controlled randomized study
Overall Study Duration	3 years
Subject Participation Duration	9 months
Objectives	Evaluate the efficacy of the RestoreX penile traction device in preventing loss of penile length in men undergoing prostatectomy
Number of Subjects	90
Diagnosis and Main Inclusion Criteria	Men undergoing prostatectomy
Study Device	RestoreX®, penile traction therapy
Duration of Exposure	Subjects will use device for 5 months for: 30 minutes, once daily, 5 days a week OR 30 minutes, twice daily, 7 days a week After the randomized period, all subjects will be entered into an open-label phase where they may choose to use or not use the device for 3 additional months
Reference therapy	During the randomized phase, the use of the device will be compared against a control group using no traction therapy In the open label phase, results at the end of 9 months will be compared to those from baseline and at the beginning of the open label phase
Statistical Methodology	Stratification of subjects prior to randomization to assure an equal representation based on baseline penile length. Statistical comparisons will be made comparing total penile length prior to and following therapy. Comparisons of subjective questionnaire responses will also be made between groups and at the various time points captured.

1 Introduction

This document is a protocol for a human research device study. This study will be carried out in accordance with the procedures described in this protocol, applicable United States government regulations and Mayo Clinic policies and procedures.

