1.2 Investigational Device

RestoreX is a PTT device developed by PathRight Medical using technology licensed from the Mayo Clinic. The device is classified as class I (orthotic) and does not require clinical trials to prove safety or efficacy. Mayo Clinic is currently conducting a randomized clinical trial to evaluate several clinically relevant factors including safety, comfort, and preference and to provide preliminary data on dosing and efficacy (IRB 17-001283).

The device has two functional aspects. The first is the ability to provide direct traction on the penis. The second is the ability to provide counter-bending forces, to treat conditions such as Peyronie's disease (bent penis). In the current study, only the direct traction aspects of the device will be investigated.

Men randomized to treatment will be recommended to utilize the device for 5 months for 30 minutes, once daily, 5 days per week or 30 minutes, twice daily, 7 days per week after undergoing a prostatectomy.

After the initial randomized phase, all patients will enter an open-label phase where they may use the device as little or as much as they choose for a period of 6 months.

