2.1 Primary Objective

1. The primary objective is to assess penile length pre and post completion of RestoreX® traction therapy compared to control groups (no treatment) of subjects who have undergone a prostatectomy.

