5.2 Statistical Analysis

Analyses will be performed using comparisons within patients of same baseline penile stretch length and between groupings of varying lengths. Comparison of penile length between traction and no traction will be made, as well as reviewing historical records to increase statistical power. Comparison of length from baseline to post-traction for individual participants will also be reviewed.

The data will also be analyzed in three ways: 1- with all patients included, regardless of their compliance to utilize the device for the recommended treatment time, 2- with patients excluded if they failed to achieve 90% compliance with the recommended duration of treatment, 3- with patients excluded if they failed to achieve 80% compliance with the recommended duration of treatment.

Comparisons will also be made on other subjective and objective variables obtained including number of adverse events, complications, subjective responses to questionnaires, or

other information. All data will be normalized based on pre-operative stretched penile length.

6 Safety and Adverse Events

Definition of Adverse Event

Unanticipated Problems Involving Risk to Subjects or Others (UPIRTSO) - any unanticipated problem or adverse event that meets the following three criteria:

Serious: Serious problems or events that results in significant harm, (which may be physical, psychological, financial, social, economic, or legal) or increased risk for the subject or others (including individuals who are not research subjects). These include: (1) death; (2) life threatening adverse experience; (3) hospitalization - inpatient, new, or prolonged; (4) disability/incapacity - persistent or significant; (5) breach of confidentiality and (6) other problems, events, or new information (i.e. publications, interim findings, product labeling change) that in the opinion of the local investigator may adversely affect the rights, safety, or welfare of the subjects or others, or substantially compromise the research data, AND

Unanticipated: (i.e. unexpected) problems or events are those that are not already described as potential risks in the protocol, consent document, not listed in the Investigator's Brochure, or not part of an underlying disease. A problem or event is "unanticipated" when it was unforeseeable at the time of its occurrence. A problem or event is "unanticipated" when it occurs at an increased frequency or at an increased severity than expected, AND

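### Section 5.2 plans three analyses by compliance without saying which decides efficacy, and two of them are not randomised comparisons

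*Combined protocol and SAP*

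**What the plan says.** Section 5.2 of the combined protocol and SAP states that "Comparison of penile length between traction and no traction will be made", without naming a population. Later it adds "The data will also be analyzed in three ways" and lists them. The first keeps everyone; in the plan's words it is done "with all patients included, regardless of their compliance to utilize the device for the recommended treatment time". The second drops men who used the device too little, and is run "with patients excluded if they failed to achieve 90% compliance with the recommended duration of treatment". The third applies the same kind of exclusion with the bar lowered to 80%.

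None of these is called primary, supportive or sensitivity, and no arm is named for the exclusions. The other places where a rule might stand do not give one. Section 2.1 begins "The primary objective is to assess penile length pre and post completion of" the device therapy and compares this with untreated controls, but names no analysis population. The Study Summary says only "Statistical comparisons will be made comparing total penile length prior to and following therapy". Section 1.2 ties the recommended use to one group: "Men randomized to treatment will be recommended to utilize the device for 5 months".

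**The concern.** If the three analyses disagree, the plan has no rule for which one answers the primary objective, and the choice could be made after the results are seen. Section 8.2 records that the Primary Investigator invented the device, and section 5.1 allows people associated with the device company to help with analysis. Both make a choice fixed in advance more valuable.

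Two of the three analyses also appear to drop men from the traction arms only, on the basis of behaviour after randomisation. If men who would have kept more length anyway also comply better, a useless device looks helpful. If men with more shortening comply better, a real benefit can be hidden.

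**Working it through.** **Step 1. Who can be excluded.** In the randomised phase:

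| Item | Traction arms | Control arm | Section |
|---|---|---|---|
| Recommended duration | yes | none (no treatment) | 1.2, 3.5 |
| Device supplied | yes | no | 3.6 |
| Usage journal or diary | from baseline | from the 6-month visit, on entering open label | 3.5, 4.2, 4.3 |

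Table 1 marks a baseline diary without naming an arm, but section 4.2 limits it to the treatment group. If controls were instead counted as failing the bar, the whole control arm would go and no comparison would remain. The workable reading is that only traction men are excluded.

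**Step 2. The plan's own figure.** 3 arms × 30 = 90, as section 3.4 states, so 60 traction and 30 control. The plan gives no alpha, test, SD, effect size or compliance rate, so everything from Step 4 on rests on assumptions.

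**Step 3. The bars differ by arm.** Reading compliance as minutes, the once-daily schedule is 30 × 5 = 150 min/week and the twice-daily schedule is 30 × 2 × 7 = 420 min/week. The 90% bar is 135 and 378 min/week, and the 80% bar is 120 and 336. The exclusions could remove different shares of the two traction arms.

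**Step 4. Bias with no device effect.** Let the outcome have SD 1 and correlate r with a normal compliance score, and drop the lowest fraction f of traction men. The retained traction mean minus the control mean is r × φ(z_f)/(1 − f), where z_f is the f-quantile of the standard normal. With r = 0.3:

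- f = 0.50 (90% bar): 0.3 × 0.399/0.50 = 0.239 SD
- f = 0.35 (80% bar): 0.3 × 0.370/0.65 = 0.171 SD

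Simulation with 40,000 null trials gives 0.237 and 0.169.

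**Step 5. Rejection rate at an assumed two-sided 0.05.** SE = √(1/n_T + 1/30), with n_T the traction men retained.

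- 90% bar, n_T = 30: SE = 0.258 and 0.239/0.258 = 0.93, so rejection is about P(Z > 1.03) + P(Z < −2.89) = 15%.
- 80% bar, n_T = 39: SE = 0.243 and 0.171/0.243 = 0.70, so rejection is about P(Z > 1.26) + P(Z < −2.66) = 11%.

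Simulated t-tests give 15.2% and 10.8%. The all-patients analysis stays at 4.8% to 5.1%.

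**Step 6. Range of assumptions (simulated, no true effect).**

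| Failing 90% / 80% bar | r | Bias, SD | Rejection | Any of the three |
|---|---|---|---|---|
| 30% / 20% | 0.1 | 0.05 / 0.04 | 5.3% / 5.1% | 7.6% |
| 20% / 10% | 0.3 | 0.10 / 0.06 | 7.3% / 5.7% | 9.2% |
| 30% / 20% | 0.3 | 0.15 / 0.11 | 10% / 7% | 12% |
| Once-daily 30% / 20%, twice-daily 70% / 50% | 0.3 | 0.21 / 0.16 | 12% / 10% | 16% |
| 50% / 35% | 0.3 | 0.24 / 0.17 | 15% / 11% | 19% |
| 50% / 35% | −0.3 | −0.24 / −0.17 | 15% / 11% | 19% |
| 70% / 50% | 0.3 | 0.35 / 0.24 | 21% / 15% | 26% |

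At 50%/35% failing, the any-of-three rate is 8% at r = 0, 13% at ±0.2 and 27% at ±0.4. It matters only if any one of the analyses could be taken as the answer, and it counts results in either direction. At r = 0.3, 16.1% of trials favour traction. At r = −0.3, 2.4% favour traction and 16.2% favour control.

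**Step 7. Does the all-patients analysis hold its 5%?** Section 3.5 lets men who cannot travel mail questionnaires, so some will have no length measurement.

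| Missing lengths, traction v control | All-patients rejection |
|---|---|
| 20% v 20%, at random | 5.1% |
| 30% v 10%, at random | 4.9% |
| 20% v 20%, related to outcome alike (r = 0.3) | 5.1% |
| 30% v 10%, related to outcome alike (r = 0.3) | 6.6% |
| 20% v 20%, related in opposite directions (r = 0.3 v −0.3) | 13.4% |

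**The case against.** The strongest reply is that this is silence, not a stated parity. The all-patients analysis is planned and listed first, the two cut-offs are fixed in advance, and compliance is itself a secondary objective (section 2.2). Readers who see all three results would see any disagreement. Part of this stands: the compliance sets have a descriptive use and should stay. But order in a list is not a rule, and nothing else in the document supplies one.

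A second reply is that the traction-only exclusion is inferred, and that section 5.2 also plans before-and-after comparisons within men, where restriction by compliance would be descriptive. It is an inference, but the only alternative found empties the control arm. Section 5.2 does not confine the three sets to within-man comparisons.

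Third, the sizes depend on assumed inputs. That is right, and the first rows of the Step 6 table show little inflation under mild assumptions. Comparing each traction arm separately with control (30 v 30) would lower the 19% to about 15%. The fault does not depend on these figures, because selection after randomisation in one group only is not a randomised comparison.

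Fourth, this is a 90-man investigator-initiated study with no stated alpha or success criterion. It still has a primary objective that compares traction with control, and needs one analysis to answer it.

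Finally, the all-patients analysis can itself be biased by missing lengths. That stands, but it is a separate gap and does not favour the compliance sets.

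**Conclusion.** The concern holds and should be fixed before analysis. No deciding analysis is named, and two of the three candidates compare traction men selected after randomisation with unselected controls. The direction and size of the bias cannot be known from the documents. Under no true effect, and depending on assumed compliance and correlation, the Step 6 settings give a bias from about 0.04 to 0.35 SD in either direction and rejection from about 5% to 21%. The all-patients analysis keeps about 5% unless missing lengths relate to outcome differently by arm, or are both outcome-related and unequal in number.

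**What to change.** Add to section 5.2:

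> All randomised men, analysed as assigned regardless of device use, are the primary analysis population and the basis for the efficacy conclusion. The 90% and 80% compliance analyses are exploratory. They retain all controls, exclude traction men only, and are not randomised comparisons. The number excluded will be reported for each traction arm.

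This settles the population only. The visit, pooling of the traction arms, test, use of historical records, handling of missing lengths and exact definition of compliance remain separate matters.

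The change needs no new data or visits. Its price is dilution and lower power if non-compliers gain nothing. With 60 v 30 and 88 df, 0.633 SD gives 80% power at full use. At 30% non-compliance the effect is 0.7 × 0.633 = 0.443 SD, with 50% power. At 50% it is 0.5 × 0.633 = 0.317 SD, with 29% power (27% when the added variance from mixing users and non-users is modelled).

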2.2 Secondary Objectives

1. Compare patient compliance with traction device.
2. Compare patient reported satisfaction with use of traction device.
3. Evaluate any adverse events (AEs) with use of RestoreX® for penile lengthening.
4. Compare the rate of Peyronie's disease development among groups
5. Compare patient satisfaction scores including satisfaction with overall penile length.
6. Evaluate and compare patient erectile function among groups
7. Compare penile length outcomes pre- and post-open phase traction therapy
8. Evaluate the duration of treatment utilized during the open phase of treatment
9. Review associations between pre-surgical factors (demographics, disease-specific factors, and standardized questionnaires) and outcomes

3 Study Design

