3.5 Study Schema

Prior to surgery, data will be recorded by the surgeon using the current standard of care questionnaires (EPIC-50, IIEF-15 disease specific variables, and demographics).

Following surgery, patients will be seen in the clinic based on the standard routine clinical practice for their catheter removal (approximately 1-3 weeks post-prostatectomy). At this time, and after the patient has consented, they will undergo initial study penile length assessments (described later in the protocol) and be educated on how to use the device properly by a trained nurse. Patients will then be given a baseline questionnaire to complete. In some cases, patients may not have been provided the IIEF-15 questionnaire prior to surgery. For these patients that have not yet filled out this questionnaire and had their data recorded in their records, they will instead receive the IIEF-15 questionnaire during this baseline visit.

Once consent and study assessments are completed, the patients will be randomized into one of three groups:

1. PTT for 30 min 1x/day, 5 days/week
2. PTT for 30 min 2x/day, 7 days/week
3. Control (no treatment)

Patients in the treatment arm will record a daily journal of their usage of the device. Patients will then begin using the device 4 weeks after surgery as instructed for the times appropriate to their group. This ensures adequate time for the patient to recover from their procedure before beginning to use the device. The study coordinator will call the patient to remind them to begin using the device.

After 5 months of using the device (+1.5 months permitted), patients will return for subsequent assessments (see below) and a follow-up questionnaire. At this time, patients will be encouraged to report any adverse events. They will also be requested to bring their device back to the clinic to review proper usage and any questions on the device. After completion of the subsequent assessments, patients will begin a 3-month, open-label phase of the trial. During this period, the patients will be allowed to use the device for 30 minutes at a time, with a frequency to be determined by the patient.

After completion of the 3-month open-phase portion of the trial, patients will return to the clinic to undergo final assessments, which are identical to the 6-month assessments. Patients will then be encouraged to self-report any additional adverse events (AE's) that they encounter over the subsequent 6 months.

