4.2 Baseline Assessment

- Participant consented (if they were not originally consented at the pre-operative appointment)
- Obtained prior to randomization at time of catheter removal (part of standard care)

- Objective assessments
 - Penile length – measured from pubic symphysis to glanular corona
- Subjective questionnaires (attached)
 - Disease specific history
 - IIEF-15 (for patients who have not completed pre-operatively)
- Device usage diary provided for treatment group

4.3 6 Month Visit

- Penile length assessment
- Questionnaires (attached)
 - 6 month
 - IIEF-15
- Device usage diary retrieved from treatment group
- Device usage diary given to all participants (enter open label phase)

4.4 9 Month Visit

- Penile length assessment
- Questionnaire
 - 9 month
 - IIEF-15
- Retrieve device usage diary

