4.5 Assessment of Length

Penile length measurements will be obtained by a member of the clinical team using a measurement from the pubic symphysis to the corona of the glans penis. Measurements will be obtained post-operatively (after catheter removal) and at the 6 and 9 month follow-ups.

See **Attachments – Device Usage Diary, Disease Specific History, IIEF-15, Questionnaire 6 Month and 9 Month**

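### Section 5.2 normalizes all data, questionnaires and adverse events included, on penile length, and states no adjustment of 6-month IIEF-15 for the man's own baseline IIEF-15

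*Combined protocol and SAP*

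**What the plan says.** The last paragraph of section 5.2 extends the analysis beyond length: "Comparisons will also be made on other subjective and objective variables obtained including number of adverse events, complications, subjective responses to questionnaires, or" other information. The next and final sentence is "All data will be normalized based on pre-operative stretched penile length". It exempts no outcome, and the plan does not say what operation is meant.

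Erectile function is a between-group objective in its own right (section 2.2, objective 6): "Evaluate and compare patient erectile function among groups". Section 4.1 lists the IIEF-15 among the pre-operative forms. Section 4.2 repeats it at the baseline visit: "IIEF-15 (for patients who have not completed pre-operatively". Section 3.5 says of men who missed the pre-operative form that "they will instead receive the IIEF-15 questionnaire during this baseline visit". The form is given again at 6 and 9 months (sections 4.3, 4.4 and Table 1).

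Two other places give questionnaires a use. The Study Summary says: "Comparisons of subjective questionnaire responses will also be made between groups and at the various time points captured". Objective 9 is: "Review associations between pre-surgical factors (demographics, disease-specific factors, and standardized questionnaires) and outcomes". Neither describes a comparison of randomised arms adjusted for the baseline score.

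**The concern.** Nothing in the documents suggests that erectile function, satisfaction or a count of adverse events is proportional to penile length. A rule that ties those outcomes to length needs a reason, and none is given. The natural baseline variable for a man's 6-month IIEF-15 is his own earlier IIEF-15. The trial schedules both, and section 5.2 does not bring them together.

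Two things are at stake for objective 6. The first is the scale on which erectile function is reported, which depends on an undefined word. The second is precision, which matters with 30 men per arm.

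The sentence has a further difficulty. It refers to a pre-operative length, but section 4.5 schedules none: "Measurements will be obtained post-operatively (after catheter removal) and at the 6 and 9 month follow-ups". Changing which length is used would not make length a suitable scale for questionnaires or events.

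**Working it through.** **Inputs from the documents.** 30 men per arm, three arms, 3 × 30 = 90 (section 3.4). Length strata are <10, 10–13, 13.1–16 and >16 cm (section 3.6). No alpha, power, effect size, SD, correlation or CV is given for any outcome, so the sample size cannot be reproduced from design inputs.

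**Assumptions.** Two-sided alpha 5%. True difference 0.6 SD between one traction arm and control. Baseline to follow-up correlation ρ of 0.3, 0.5 or 0.7. CV of the score 0.3 to 0.7. CV of length 0.12 to 0.19. Length independent of the score.

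**Step 1: reading 'normalized' as division.** Two men with an assumed score of 20 and lengths of 10 and 16 cm become 20/10 = 2.00 and 20/16 = 1.25. Since 2.00/1.25 = 1.60, they differ by 60% although their function is the same.

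For noise, score/length was simulated with 0.6 SD added to the score in the treated arm. Each cell gives the variance inflation relative to the squared effect, (0.6 / standardised effect on the ratio scale)², and the power at 30 v 30:

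| Score CV | Length CV 0.12 | Length CV 0.15 | Length CV 0.19 |
|---|---|---|---|
| 0.3 | 1.23; 56% | 1.38; 51% | 1.68; 43% |
| 0.5 | 1.10; 60% | 1.17; 58% | 1.31; 53% |
| 0.7 | 1.07; 62% | 1.11; 60% | 1.19; 57% |

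The unscaled score has power 64%. The penalty is small when scores vary widely and large when they do not.

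**Step 2: reading it as a covariate or stratum.** A length term unrelated to IIEF-15 uses a few degrees of freedom and adds almost no noise. The table does not apply.

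**Step 3: baseline IIEF-15, under either reading.** ANCOVA multiplies the residual SD by √(1 − ρ²). Power = Φ(0.6 × √(30/2) / √(1 − ρ²) − 1.96), where 0.6 × √15 = 2.324.

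- Unadjusted: Φ(2.324 − 1.96) = Φ(0.364) = 64%.
- ρ = 0.3: √0.91 = 0.954; Φ(2.436 − 1.96) = 68%.
- ρ = 0.5: √0.75 = 0.866; Φ(2.683 − 1.96) = 77%.
- ρ = 0.7: √0.51 = 0.714; Φ(3.254 − 1.96) = 90%.

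The equivalent unadjusted arm size is 30/(1 − ρ²): 30/0.91 = 33, 30/0.75 = 40 and 30/0.51 = 59 men. The difference detectable with 80% power falls from 0.72 SD to 0.69, 0.63 or 0.52 SD. These figures use a normal approximation and ignore the few degrees of freedom spent on covariates.

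**The case against.** **The plan may not intend division.** This stands. Section 5.2 opens with comparisons among men of like baseline length, and section 3.6 stratifies on length partly to match the groups. Those passages fit a matched or stratified meaning at least as well. A reader might infer that the trial will report IIEF-15 per centimetre, but the documents do not say so. The 60% example and the table are therefore conditional. Even under division, randomisation is stratified on length, so the main effect would be noise and not a systematic advantage to one arm.

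**The baseline score is not discarded.** This also stands. A reader might conclude that the baseline IIEF-15 is wasted, but objective 9 and the planned comparisons across time points both give it a role. What is missing is narrower: its use in the between-arm comparison for objective 6.

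**The correlation may be low.** Some men complete the form before surgery and others at catheter removal. For the first group, surgery falls between baseline and follow-up. At ρ = 0.3 the gain is only 64% to 68%. The higher figures are a range, not a forecast.

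**The adjustment does not extend to all questionnaires.** Correct. Table 1 shows the 6- and 9-month questionnaires only at those visits, so they have no matching baseline.

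**The consequence is limited.** Erectile function is one of nine secondary objectives, and section 1.4.2 expects no effect of traction on rigidity either way. An unadjusted, unscaled comparison of randomised arms would still be valid. This limits the importance of the point but does not remove it: if the aim is to show little difference, the width of the interval decides how convincing the result is, and adjustment narrows it by the factor √(1 − ρ²).

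**Conclusion.** The point holds as one of ambiguity and efficiency. As written, section 5.2 applies an undefined length normalization to questionnaire responses and adverse events, for which length is not a natural scale, and it states no baseline-adjusted analysis of IIEF-15.

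Harm from the normalization is conditional. Under division, variance rises by a factor of 1.07 to 1.68 and power falls from 64% to between 43% and 62%. Under a covariate or stratum reading there is almost no loss. The precision forgone by not using baseline IIEF-15 applies under either reading: power of 68% to 90% instead of 64%. All of these figures rest on the assumed effect, alpha, correlations and CVs, since the documents supply none.

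The documents do not support a claim that scores will certainly be distorted, that the primary length comparison is affected by this point, or that baseline IIEF-15 is the right covariate for anything other than IIEF-15.

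**What to change.** Amend section 5.2 as follows.

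- Limit the normalization sentence to length outcomes, define the operation, and state which scheduled length measurement it uses.
- Compare 6-month IIEF-15 between randomised arms by ANCOVA on the man's own baseline IIEF-15, with an indicator for whether that form was completed before or after surgery, and the length stratum. Include the interaction of the indicator with the baseline score if the slopes differ. Sections 3.5 and 4.2 place either form before randomisation, so it is a proper baseline covariate.
- Report satisfaction scores and adverse events unscaled, with no IIEF-15 adjustment.
- State a simple rule for men with no baseline form, so that they remain in the comparison.

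The cost is SAP wording and that rule. No new visit, form or participant is needed.

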3.6 Randomization Protocol

Following enrollment and completion of the initial length assessment, patients will be categorized into the appropriate strata based on their baseline stretched penile length; strata categorized as <10 cm, 10cm-13cm, 13.1cm-16cm, >16cm stretched length. Each stratum will have a separate randomization table provided such that one of three possible outcomes will occur no less frequently than every other case. This is done to better account for baseline variables that may impact outcomes and to assist with matching groupings appropriately.

The explanation of which grouping the patient is assigned will then be reviewed, and if the patient subject is assigned to the treatment group, a RestoreX® device will be provided.

4 Study Procedures

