4.1 Pre-Operative Assessments

- Captured as a function of standard care
 - EPIC-50
 - IIEF-15
 - Disease specific variables
 - Demographics
- Participant consented

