4.6 Schedule of Events

Table 1: Schedule of Events

Study Activity	Pre-operative	Baseline Assessment	6 Month	9Month
----------------	---------------	---------------------	---------	--------

		(post-operative up to 1 mo)		
Consent	X	X		
EPIC-50	X			
IIEF-15	X	X	X	X
Disease Specific History		X		
Length Assessment		X	X	X
Patient Diary Provided		X	X	
Questionnaire 6 Month			X	
Questionnaire 9Month				X

5 Statistical Plan

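### Section 5.2 normalises all data to a pre-operative stretched length that the documents neither name nor schedule, and does not define the normalisation

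*Combined protocol and SAP*

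**What the plan says.** The last sentence of 5.2 Statistical Analysis reads: "All data will be normalized based on pre-operative stretched penile length". It closes a paragraph on adverse events, complications and questionnaire responses, but its wording covers everything. It is the only adjustment rule in the statistical plan; 5.2 names no test, model or covariate.

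The data collection sections say this about length:

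- **3.5 Study Schema, before surgery.** The surgeon records data "using the current standard of care questionnaires (EPIC-50, IIEF-15 disease specific variables, and demographics". Length is not among them.
- **3.5 Study Schema, after surgery.** At the catheter-removal visit, about 1 to 3 weeks after the operation: "At this time, and after the patient has consented, they will undergo initial study penile length assessments".
- **4.1 Pre-Operative Assessments.** EPIC-50, IIEF-15, "Disease specific variables" and demographics. No length.
- **4.2 Baseline Assessment.** Length is listed here, with the timing "Obtained prior to randomization at time of catheter removal (part of standard care".
- **4.5 Assessment of Length.** "Measurements will be obtained post-operatively (after catheter removal) and at the 6 and 9 month follow-ups".
- **4.6, Table 1.** The length row has three marks: baseline (labelled "post-operative up to 1 mo"), 6 months and 9 months.
- **3.6 Randomization Protocol.** "patients will be categorized into the appropriate strata based on their baseline stretched penile length".

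Elsewhere 5.2 uses baseline as its reference: its opening sentence groups men by baseline stretched length, and it later compares each man's length from baseline to after traction.

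**The concern.** The analysis rule and the schedule point to different measurements. Read literally, the rule covers the length comparison that forms the primary objective in 2.1, and it needs a value that the schedule does not supply for any of the 90 men.

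Three things are left open:

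1. Which length takes the place of the unscheduled one.
2. What normalising means: dividing by the reference, subtracting it, or adjusting for it in a model.
3. Which outcomes the rule covers. A count of adverse events or an IIEF-15 score divided by centimetres has no interpretation.

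If these are settled after the data are in, the choice is made by people who can see which answer each reading gives. Prespecification carries extra weight here: 8.2 discloses that the Primary Investigator invented the device, and 5.1 allows people associated with its company to help with the analysis.

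**Working it through.** **Step 1. Count the scheduled lengths.** From 3.5, 4.1, 4.2, 4.5 and Table 1: 0 before surgery; 3 after it (baseline, 6 months, 9 months). Table 1 is only supporting evidence, because its pre-operative column also leaves out the demographics and disease specific variables that 4.1 lists. The firmer evidence is the two pre-operative lists and the explicit timing in 4.5.

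**Step 2. Could a pre-operative study length exist for every man?** No. Under 3.4, consent may be given up to one month after prostatectomy, and under 3.5 study length is measured after consent. A man who consents after surgery cannot have a pre-operative study measurement.

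**Step 3. Is the scheduled baseline a sound covariate?** Yes. Section 4.2 places it before randomisation and 3.6 uses it to form the strata. It also fits 2.1, which asks about length before and after traction against control, not before and after surgery.

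**Step 4. Does the form of normalising matter?** The documents give no SD, correlation, alpha, power or effect size. The sample size (30 × 3 = 90) therefore cannot be re-derived, and nothing here depends on it. The rest is illustration.

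Assumptions: baseline length X and 6-month length Y are bivariate normal with mean 12 cm and equal SD of 1.5 to 2.5 cm; correlation r is 0.5 to 0.9; traction adds a constant; strata are ignored. The sample needed relative to ANCOVA is the ratio of variances per unit of effect.

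- ANCOVA variance: SD²(1 − r²).
- Change score: 2·SD²(1 − r). Relative to ANCOVA this is 2(1 − r)/(1 − r²) = 2/(1 + r), which gives 2/1.5 = 1.33, 2/1.7 = 1.18 and 2/1.9 = 1.05 at r = 0.5, 0.7 and 0.9.
- Ratio Y/X: var(Y/X)/E[1/X]², because a constant shift d moves the mean ratio by d·E[1/X]. This was evaluated with 4 million draws. Worked case, SD 2 and r = 0.7: var(Y/X) = 0.01876 and E[1/X] = 0.08586, so 0.01876/0.08586² = 2.545. ANCOVA has 4 × 0.51 = 2.04, and 2.545/2.04 = 1.25.

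| Sample relative to ANCOVA | r = 0.5 | r = 0.7 | r = 0.9 |
|---|---|---|---|
| Change score, any SD | 1.33 | 1.18 | 1.05 |
| Ratio, SD 1.5 cm | 1.39 | 1.21 | 1.08 |
| Ratio, SD 2 cm | 1.44 | 1.25 | 1.10 |
| Ratio, SD 2.5 cm | 1.51 | 1.30 | 1.13 |

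**Step 5. Could the readings give different answers in one trial?** A simulation took 60 traction against 30 control, with assumed blocks of 3 within the strata of 3.6 and an effect set for about 79% ANCOVA power. Ratio, change and ANCOVA disagreed on p < 0.05 in 7% to 22% of trials. The upper end comes from the ratio at low correlation; change and ANCOVA alone disagreed in about 3% to 12%. With no true effect, picking the smallest p of the three was significant in about 5.5% to 6.7% of trials, against a nominal 5%.

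**The case against.** The strongest defence is that the sentence contains a one-word slip. Sections 3.6 and 5.2 both speak of baseline stretched length, and the primary objective runs from before to after traction. On that reading, one changed word cures the contradiction. This is plausible and lowers the severity. It does not remove the point: the text still needs correcting, and normalising is still undefined.

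A second defence is that a pre-operative length may exist. The disease specific variables in 4.1 are not itemised in the visible text, and the forms are attachments that are not shown. A reader might infer that no such value exists anywhere; the documents do not support that. They support only that none is named or scheduled. Historical records appear in 5.2 as a way to raise power, not as a source of participants' own earlier lengths.

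A reader might also infer that a post-operative baseline biases the randomised comparison. It does not: the baseline is taken before allocation and serves all arms alike. Nor do the calculations suggest serious false-positive inflation. The disagreement between readings is mostly lost power.

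Finally, the magnitudes rest on assumed inputs, and 3.6 does not specify blocks of 3. That stands. Only the count of 0 against 3 comes from the documents.

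**Conclusion.** The point holds as a should-fix. The plan's only adjustment rule refers to a length that the visible documents neither name nor schedule, leaves its operation undefined, and extends to outcomes where it has no meaning. The between-arm comparison remains sound once the rule is restated on the scheduled baseline. What scheduled measurements cannot give is the loss of length since before surgery. This matters for wording, because the Study Summary speaks of preventing loss of length in men undergoing prostatectomy.

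Under the assumptions in the working, choosing the ratio instead of ANCOVA costs between 8% and 51% more patients, and a change score 5% to 33% more. The documents cannot narrow these ranges.

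**What to change.** Replace the last sentence of 5.2 with, for example: *Between-arm comparisons of 6-month penile length (cm) use ANCOVA with baseline (post-operative, pre-randomisation) stretched length as a continuous covariate and randomisation stratum as a factor; adverse events and questionnaire scores are not scaled to length.*

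Then:

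- State that this model governs the length comparison, and that the comparisons within and between baseline-length groups in the first sentence of 5.2 are supportive.
- Call the covariate baseline length, not catheter-removal length. A man who consents after catheter removal but within the one-month window may have no study length from that visit.
- Report within-arm change as change from the post-operative baseline, and state that loss since before surgery is not estimated from scheduled measurements.
- If a pre-operative length does exist in records, list it in 4.1 and Table 1.
- Give a rule for merging a sparse stratum. Under the assumed SDs, only about 0.3 to 4.7 of 90 men would exceed 16 cm.

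The cost is wording only, with no new visit or measurement. The stratum factor adds about 1% to the variance if randomisation is blocked within strata, and 2% to 4% if it is simple, under the same assumptions.

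Two matters are separate and not settled here: whether the primary contrast is pooled traction or each traction arm against control, and how to handle men followed only by mail, for whom 3.5 asks for questionnaires and the diary but no clinic length.
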